2.6.2 Statistical method of analysis

The analysis of proportion of participants tolerating a single dose of \geq 600 mg of peanut protein without dose-limiting symptoms during an open label OFC at scheduled timepoints will be summarized with number and percentage of responders at Week 52, Week 104 and Week 156 by treatment group and overall.

To evaluate for all participants who administered study treatment at home by self-administration or parent/caregiver under the second secondary endpoints analysis for overall incidence of treatment-emergent adverse events (TEAEs) and serious adverse events (TESAEs) will be summarized as per Section 2.5.2.

Summaries for change from baseline in FAQLQ, SF-36v2 and FAIM domain and total scores will also be provided by age group and responder (participants and/or parent/caregiver) at scheduled timepoints (Refer Section 2.12).

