6.5.4 Retreatment criteria

Restart of study treatment is only possible for the participants undergoing conditional discontinuation of study treatment, but becoming sensitive to the food allergen, as defined by the OFC (no longer MR) after being off-treatment.

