7.1 Discontinuation of study treatment

Discontinuation of study treatment for a participant occurs when study treatment is permanently stopped for any reason (prior to the planned completion of study treatment administration, if any) and can be initiated by either the participant or the Investigator.

The Investigator must discontinue study treatment for a given participant if, he/she believes that continuation would negatively impact the participant's well-being.

Discontinuation from study treatment is required under the following circumstances:

- Participant/guardian decision
- Pregnancy
- AEs for which continued exposure to the study drug would be detrimental
- Abnormal liver and/or renal laboratory results requiring discontinuation
- Platelets <75000 /uL
- Participant experiences a life-threatening hypersensitivity event due to any reason needing an ICU admission or intubation
- Participant experiences a serious hypersensitivity event suspected to be related to study treatment
- Use of prohibited treatment as per recommendations in the prohibited treatment section
- Any situation in which continued study participation might result in a safety risk to the participant
- Following emergency unblinding

If discontinuation from study treatment occurs, the Investigator should make a reasonable effort to understand the primary reason for the participant's discontinuation from study treatment and record this information.

Participants who discontinue from study treatment agree to return for the end of treatment and follow-up visits indicated in Section 1.3 Schedule of Activities.

If the participant cannot or is unwilling to attend any visit(s), the site staff should maintain regular telephone contact with the participant, or with a person pre-designated by the participant. This telephone contact should preferably be done according to the study visit schedule. Participants who discontinue study treatment will no longer undergo any OFC that may be planned on the remaining visit(s). After discontinuation from study treatment, at a minimum, in abbreviated visits, the following data should be collected at clinic visits or via telephone/email contact:

- New / concomitant treatments
- Adverse Events / Serious Adverse Events

The Investigator must also contact the IRT to register the participant's discontinuation from study treatment.

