CRF Case Report/Record Form (paper or electronic)

CRO Contract research organization

CSR Clinical study report
CV Coefficient of variation

DBL Database Lock

DBPCFC Double Blind Placebo Controlled Food Challenge

DLS Dose limiting symptom
EAIR Exposure adjusted
ECG Electrocardiogram

eCRF Electronic case report form
eCRS Electronic case retrieval strategy

EOS End of study

FAIM Food Allergy Independent Measure
FAQLQ Food Allergy Quality of Life Questionnaire

FAS Full Analysis Set

FcεRI IgE (high affinity) receptor

h Hour HR Heart rate

HRQoL Health-Related Quality of Life

IgE Immunoglobulin E (specific and un-specific for the study allergen)

IgG Immunoglobulin G
IS Independent Statistician

L Liter

CCI

MedDRA Medical dictionary for regulatory activities

mg Milligram(s)
mL Milliliter(s)
mm Millimeter

mmHg Blood pressure unit millimeters of mercury

MR Maximum responder

ms Millisecond

OFC Oral Food Challenge PD Pharmacodynamic(s)

CC

PRO	Patient Reported Outcomes
PT	Preferred term
q4W	Every 4 weeks
RR	Responder rate
SAE	Serious Adverse Event
SAF	Safety analysis set
SAP	Statistical analysis plan
SC	Subcutaneous
SCq4W	Subcutaneous injection every 4 weeks
SD	Standard deviation
CCI	
SMQ	Standardized MedDRA Query
SOC	System organ class
SPT	Skin Prick Test
TEAE	Treatment-emergent adverse events
TESAE	Treatment-emergent serious adverse events
Total IgE	Drug-bound and free IgE
μL	Microliter

1 Introduction

The purpose of this Statistical Analysis Plan (SAP) is to describe the statistical analyses mentioned in version of the Phase 3 study CQGE031G12303B protocol. This document covers the statistical and analytical plans for the Clinical Study Report (CSR).

After thorough consideration, Novartis decided to terminate the study early. This was a consequence of a broader Novartis company strategic decision and was by no means due to the detection of any potential safety signal. Due to the early termination, the scope of analysis will be limited.

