2.5 Analysis supporting primary objective(s)

2.5.1 Primary safety endpoint(s)

The primary objective of the study is to assess the long-term safety and tolerability of ligelizumab in participants with food allergy for an additional three-year period after a core study.

Page 15 of 28 Study No. CQGE031G12303B

Primary endpoints are overall incidence and exposure-adjusted occurrence rates (EAOR) of treatment-emergent adverse events (TEAEs) and serious adverse events (TESAEs), however, due to early termination of the study, EAOR will not be calculated.

TEAEs are defined as events that either:

- 1) Where an AE either started after the first dose of extension study treatment and within 16 weeks after the last administered study treatment dose or
- 2) began prior to the first dose of study treatment but increased in severity (based on preferred term) within 16 weeks after the last study treatment.

All participants enrolled into the extension study, regardless of which preceding studies they came from, will be included in the safety analysis. All listings and tables will be presented by treatment dose. All data will be included in the analysis, regardless of rescue medication use.

This analysis will be based on SAF-1.

For all adverse events tables the events that the investigator classified as reactions associated to the Oral Food Challenge (OFC)or Skin Prick Test (SPT) will not be included in reporting of treatment-emergent adverse events (TEAEs).

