2.5.2.1 Exposure-Adjusted Incidence rate and 95% confidence interval

The EAIR is defined as the number of participants with a specific event divided by the total exposure-time among the participants in the study group. That is, the EAIR is calculated as:

 $EAIR = n / \Sigma t_i$, where n is the number of participants having the i^{th} type event, and t_i is a participant's exposure time and defined as the shortest of the following:

- 1. Time to the first episode of the i^{th} type event (if the event occurs),
- 2. Time to the end of observation period, or
- 3. duration of study treatment plus the 16-week washout period (approximately corresponding to five half-lives) after last treatment dose

The total exposure time of all participants in a treatment group is Σ t_i . The EAIR is interpreted as the number of events occurring in a population per unit time. The exact Poisson 95% confidence interval for the EAIR will be provided as well, where an exact $100*(1-\alpha)\%$ confidence interval will be derived as follows (Garwood 1936, Sahai and Khurshid 1993):

- Lower confidence limit $L = \frac{0.5C_{\alpha/2,2n}}{\sum t_i}$ for n>0, 0 otherwise,
- Upper confidence limit $U = \frac{0.5C_{1-\alpha/2,2n+2}}{\sum t_i}$,

where $C_{\alpha,k}$ is the α th quantile of the Chi-square distribution with k degrees of freedom.

Whenever applicable, exposure adjusted incidence rates will be provided for the type as below:

- 1. TEAE and TESAE: Primary SOC level, PT level
- 2. Further safety analyses are defined in safety analyses (Section 2.8)

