2.5.2.2 Adverse Events (AEs)

The following treatment-emergent AE summaries will be provided by overall and by treatment group for the Safety Set 1 (SAF-1), presented by dose and cumulative duration of exposure:

- Overview of all TEAEs: Number of participants with at least one (Any AE, Any SAE, Any AE related to study drug, Any AE leading to discontinuation of study treatment, Deaths etc.)
- TEAEs by primary system organ class and preferred term,
- TEAEs by primary Standardized MedDRA Query (SMQ) and preferred term,
- TEAEs by primary system organ class, preferred term and maximum severity,
- TESAEs by primary system organ class and preferred term,
- TEAEs leading to permanent discontinuation of study-drug by primary system organ class and preferred term,
- Treatment Emergent Adverse events of special interest (AESI),
- Study treatment-related adverse events by primary system organ class and preferred term,
- Deaths by primary system organ class and preferred term including listing of deaths,

If a participant reported more than one AE with the same preferred term, the AE with the greatest severity will be presented. If a participant reported more than one AE within the same primary system organ class, the participant will be counted only once with the greatest severity at the system organ class level, where applicable.

Separate summaries will be provided for study treatment-related adverse events, death, serious adverse events, and other significant adverse events leading to discontinuation.

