2.6 Analysis supporting secondary objectives

2.6.1 Secondary endpoint(s)

Secondary objective [1] is to describe the long-term efficacy of ligelizumab as measured by the tolerance of an allergen food protein during an open-label OFC at scheduled timepoints.

To satisfy the above secondary objectives the following endpoint will be taken into consideration:

Proportion of participants tolerating a single dose of \geq 600 mg of peanut protein without dose-limiting symptoms during an open label OFC at scheduled timepoints. This analysis will be based on FAS.

Secondary objective [2] is to assess the safety and tolerability of ligelizumab in all participants who administered study treatment at home by self-administration or parent/caregiver.

To satisfy the above secondary objectives the following endpoint will be taken into consideration:

Overall incidence rates of treatment emergent-AEs and SAEs will be analysis based on SAF-1.

Secondary objective [3] is to assess the long-term impact of ligelizumab on the health-related quality of life (HRQoL) of patients with food allergy.

To satisfy the above secondary objectives the following endpoint will be taken into consideration:

Summaries of total scores in the FAQLQ, FAIM, and SF-36v2 by age group and responder (participants and/or parent/caregiver) at scheduled timepoints.

This analysis will be based on FAS and latest available value at each visit will be used for summary.

Note: SF-36v2 completed by adults only.

For all efficacy endpoints, if missing Week 52-OFC assessments, Week 156-OFC assessments performed within 380 days (inclusive) after first extension dose date will be considered as Week 52-OFC assessments.

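### On the visible text, the home-administration safety table selects home users but counts events and person-time from the first extension dose in any setting: 28 weeks and seven on-site doses for someone going home at Week 28

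*SAP*

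**What the plan says.** SAP 2.6.1 sets the analysis set for the home objective: "Overall incidence rates of treatment emergent-AEs and SAEs will be analysis based on SAF-1". SAP 2.6.2 narrows this to participants who dosed at home, by themselves or through a caregiver, and takes its method from the primary safety analysis: "overall incidence of treatment-emergent adverse events (TEAEs) and serious adverse events (TESAEs) will be summarized as per Section 2.5.2". SAP 2.5.2 supplies crude incidence and, alongside it, the exposure-adjusted incidence rate (EAIR).

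The timing rules come with that method. Under SAP 2.5.1 a treatment-emergent event (TEAE) is one of the following kind, or a worsening of an earlier one: "Where an AE either started after the first dose of extension study treatment and within 16 weeks after the last administered study treatment dose". Under SAP 2.5.2.1, person-time stops at the first event of the type, at the end of observation, or at "duration of study treatment plus the 16-week washout period (approximately corresponding to five half-lives) after last treatment dose", whichever is shortest. SAP 2.4.1 measures treatment duration from the first known dose. None of these depends on where the dose was given.

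Protocol 4.1.3 puts training injections on site at Weeks 16, 20 and 24, and the first home dose at Week 28 at the earliest. Those who start later go home at Week 68 or 120. The same section says that the study will assess the drug's safety when given in the home setting.

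**The concern.** A table headed as home-administration safety will be read as describing what happens when dosing leaves the clinic. Here it would mix clinic and home time in the same people, with three effects.

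- **Crude incidence** includes events that occurred before any home injection.
- **First-episode counting** means that a clinic-phase event stops the clock for that event type, so a later home-phase event of the same type is never seen.
- **Pre-home time is selected.** Protocol 7.1 requires permanent discontinuation in listed situations, for example "Participant experiences a serious hypersensitivity event suspected to be related to study treatment". Protocol 6.5.4 adds: "Restart of study treatment is only possible for the participants undergoing conditional discontinuation of study treatment". Someone with such an event before home start therefore never becomes a home user if the protocol is followed. For those events the pre-home weeks add person-time but cannot add a case.

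**Working it through.** **Schedule.** Table 4-2 has 40 doses: 23 at home and 17 on site. Seven of the on-site doses come before Week 28 (Day 1, Weeks 4, 8, 12, 16, 20, 24) and ten after. Week 28 is Day 28 × 7 = 196, as the table states. Three of the seven are training injections, but they are still given on site.

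**Share of the window before home use.** Formula: lead-in / (last dose − first dose + 16), in weeks, with no earlier event.

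| First dose | Home start | Last dose | Share |
|---|---|---|---|
| Day 1 | Week 28 | Week 52 | 28/68 = 41% |
| Day 1 | Week 28 | Week 104 | 28/120 = 23% |
| Day 1 | Week 28 | Week 156 | 28/172 = 16% |
| Day 1 | Week 68 | Week 156 | 68/172 = 40% |
| Day 1 | Week 120 | Week 156 | 120/172 = 70% |
| Week 52 | Week 68 | Week 104 | 16/68 = 24% |

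The last-dose weeks are assumed. The visible EAIR text gives no explicit time origin; I infer it from the TEAE definition and from SAP 2.4.1. If the 28 days that SAP 2.4.1 adds to treatment duration are also counted, 41% becomes 28/72 = 39%.

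**Crude incidence.** Week 28 home start, last dose Week 52, constant event rate (assumed), 52 weeks per year. Removing only the pre-home time shortens the window from 68 to 40 weeks.

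- At 0.5 per year: 1 − exp(−0.5 × 68/52) = 48% against 1 − exp(−0.5 × 40/52) = 32%.
- At 0.1 per year: 1 − exp(−0.1 × 68/52) = 12.3% against 1 − exp(−0.1 × 40/52) = 7.4%.

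**Clock stopped before any home injection.** 1 − exp(−0.1 × 28/52) = 5% of participants at 0.1 per year, and 1 − exp(−0.5 × 28/52) = 24% at 0.5.

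**EAIR for treatment-ending events.** None occur in a lead-in of p weeks. A constant rate L then applies for h weeks:

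EAIR = (1 − exp(−L·h/52)) / (p/52 + (1 − exp(−L·h/52))/L)

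With L = 0.01 per year (assumed) and p = 28:

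- h = 40 (last dose Week 52): 0.00766 / (0.538 + 0.766) = 0.00587, or 59% of L.
- h = 144 (last dose Week 156): 0.02731 / (0.538 + 2.731) = 0.00835, or 84% of L.

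**EAIR for other events.** If the rate is constant across settings, the EAIR is unbiased. If it rises from 0.1 to 0.2 per year at home start (assumed; 28 then 40 weeks), the expected participants with an event are 0.0524 + 0.1351 = 0.1875, over 0.524 + 0.676 = 1.200 person-years. The pooled rate is 0.156, so 56% of the increase shows.

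**The case against.** **Text not visible.** SAP 2.1.1 is blacked out, and the text on analysis sets and subgroups (2.2) cannot be read either. A home period may be defined there. A reader might infer that the plan has none; the documents do not support that. What stands is that 2.6.2 refers only to 2.5.2.

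**The objective is about persons.** It asks about all participants who dosed at home, and the planned table answers that. This stands, and is the reason to keep the table. It does not meet the setting-based aim in Protocol 4.1.3.

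**Exposure bands.** TEAE summaries are to be "presented by dose and cumulative duration of exposure". Home start differs between people (Week 28, 68, 120 or deferred), so these bands do not separate home from clinic.

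**No matching rate is visibly planned.** A reader might infer that the SAP plans a biased EAIR for serious, suspected-related hypersensitivity. It does not visibly do so. SAP 2.5.2.1 lists EAIRs for TEAEs and serious TEAEs by organ class and preferred term. SAP 2.5.2.3 reports events of special interest as number and percentage. The 59% and 84% therefore apply only to the treatment-ending part of a preferred-term rate. EAIR itself enters objective 2 only through the reference to 2.5.2.

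**Few events.** SAP Section 3 expects about 200 participants in all. Even if every one had 40 home weeks at 0.01 per year, 200 × 40/52 × 0.01 = 1.5 events would be expected. The exact Poisson interval for one event runs from 0.03 to 5.6 events, far wider than a factor of 0.59. This stands: the downward bias is systematic but would be hard to see.

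**Limited scope.** The SAP's introduction says: "Due to the early termination, the scope of analysis will be limited". The analysis is descriptive. But early termination also makes short follow-up more likely, and there the pre-home share is largest. It makes the Week 104 and Week 156 examples less likely.

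**Conclusion.** The point holds on the visible text. For a Day 1 starter going home at Week 28, the home table includes 28 weeks and seven on-site doses, between 16% and 41% of the window for last doses from Week 156 back to Week 52. Crude incidence and first-episode counting are affected for every event type. The downward bias in the EAIR is confined to events that end treatment, assumes that the protocol's discontinuation and restart rules are followed, and will rest on few events.

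A reader might conclude that the table cannot inform home safety at all. That goes too far. In the same examples, 59% to 84% of the window follows home start, dose records are to be listed, and adjudicated anaphylaxis cases are to be listed individually. The table dilutes the home-setting evaluation; it does not empty it. The weeks follow from the protocol schedule. The event rates and last-dose weeks are assumptions.

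**What to change.** In SAP 2.6.2:

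1. Keep the planned table and label it as whole-extension experience of home users.
2. Add a descriptive table of TEAEs and serious TEAEs, crude and EAIR, whose event window and person-time open at each participant's first home injection. Close them 16 weeks after the last home injection, or earlier at the first on-site dose after permanent reversion to site or after restart from conditional discontinuation. Routine scheduled on-site doses do not close the window.
3. Flag each event by the setting of the most recent dose, derived from dose-administration, visit and home dosing-log dates.
4. If SAP 2.1 or 2.2 already defines a home period, cite it here instead.

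No change to study conduct is needed. The cost is SAP wording and some programming. Setting cannot simply be read off the example diary in Protocol 10.9.10, which asks who injected and not where, and Protocol 6.2.3.1 lets home users self-inject under supervision at site visits. The added table has a shorter window and fewer events. With a last home dose at Week 48 and an on-site dose at Week 52, its window runs from Week 28 to Week 64, or 36 weeks instead of 68. Of the 32 weeks lost, 28 are pre-home time and 4 come from the closing rule.

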2.6.3 Handling of intercurrent events

Not Applicable.

2.6.4 Handling of missing values not related to intercurrent event

Missing data will not be imputed.

2.6.5 Sensitivity analyses

Not Applicable.

2.7 Exploratory analyses

2.8 Safety analyses

All safety endpoints i.e. AEs, laboratory data and vital signs will be conducted on SAF-1, only wherever required summary and listings will be provided on SAF-2. All listings and tables will be presented by treatment group.

2.8.1 Requirements of ClinicalTrials.gov and EudraCT

For the legal requirements of ClinicalTrials.gov and EudraCT, two required tables on treatment emergent AEs: non-serious AEs with an incidence greater than 3%, and deaths and serious AEs (SAEs) including the events suspected to be related to study treatment, will be provided by SOC and PT on the Safety Set. The cut-off of 3% can be re-evaluated based on number of patients.

If for the same patient, several consecutive AEs (irrespective of study treatment causality, seriousness, and severity) occurred with the same SOC and PT:

- a single occurrence will be counted if there is ≤ 1 day gap between the end date of the preceding AE and the start date of the consecutive AE
- more than one occurrence will be counted if there is > 1 day gap between the end date of the preceding AE and the start date of the consecutive AE

For occurrence, the presence of at least one SAE / SAE suspected to be related to study treatment / non-SAE has to be checked in a block e.g., among AEs in a \leq 1 day gap block, if at least one SAE is occurring, then one occurrence is calculated for that SAE.

2.8.2 Deaths

The number of deaths resulting from TEAEs will be summarized by SOC and PT. All the deaths in the clinical database including those occurring during screening will be listed.

2.8.3 Laboratory data

For selected parameters (Hematology & Clinical Chemistry) Shift tables using the low/normal/high (low and high) classification will be used to compare baseline to the worst post-baseline value. For the shift tables, the normal laboratory ranges will be used to evaluate whether the worst post-baseline value was normal, low, or high relative to whether or not the baseline value was normal, low or high. These summaries will be presented by laboratory parameter and visit.

Additionally, all-laboratory data will be listed.

2.8.4 Other safety data

2.8.4.1 Vital signs

Summary of abnormal vital signs will be provided for SAF-1 based on following criteria.

Participants with notable vital signs as defined below will be listed.

For adults:

Notable values for vital signs for adults are:

• Heart rate of < 60 and > 100 bpm

- Systolic blood pressure of < 90 and ≥ 140 mmHg
- Diastolic blood pressure of < 60 and ≥ 90 mmHg
- For children (6-11 years) and adolescents, the notable values are described in Table 2-1:

Table 2-1 Notable values for Heart Rate (HR) and Blood Pressure in children and adolescents

	HR (bpm)					
Age range	Low		High			
6-8 years	<74		>111			
8-12 years	<67		>103			
12-15 years	<62		>96			
≥ 15 years	<58		>92			
	Blood pressu	re (mmHg)				
Age (years)	Boys		Girls			
6	105	66	105	67		
7	400	00	400	00		

Age (years)	Boys		Girls		
6	105	66	105	67	
7	106	68	106	68	
8	107	69	107	69	
9	107	70	108	71	
10	108	72	109	72	
11	110	74	111	74	
12	113	75	114	75	
13	120	80	120	80	

Heart Rate (HR) Adapted from Fleming et al 2011; Blood Pressure (BP) adapted from Flynn et al 2017

